PATH-MCI aims to reduce negative emotions and promote positive emotions associated with depression, including depressed mood, hopelessness, helplessness, guilt, anxiety, and anhedonia. The tools to achieve emotion regulation are: a) a hands-on problem-solving approach, simplified from Problem Solving Therapy (PST); b) compensatory strategies and environmental adaptations to bypass mild cognitive deficits or functional and behavioral limitations, due to depression or physical disability; c) careful integration of significant other involvement; and d) engagement in pleasurable activities. Using these tools, PATH-MCI can create an environmentally friendly "ecosystem" that decreases everyday stressors, empowers patients, instills hope, and promotes emotion regulation.

A simplified problem-solving approach from PST was chosen because: a) PST has been found effective in cognitively-intact depressed elders and in depressed elders with mild executive dysfunction; b) PST creates a forum within which patients and therapists can collaboratively set treatment goals, and it provides the structure and the process for patient problem-solving pertinent to decreasing depressive symptoms and functional limitations; and c) problem-solving strategies can be appropriately modified, and when this is done, they can help remedy behavioral limitations resulting from depression and mild cognitive impairment. Because solutions of problems may not necessarily reduce depression, the focus of PATH-MCI's problem-solving approach is to reduce negative emotions and promote positive emotions that are associated with the specific problem. To achieve emotion regulation, the PATH- MCI therapist guides the patient to find the best possible solution but also helps the patient adapt, if the solution is not satisfactory.

Consistent with the NIMH *Objective 3* for a person-centered approach using RDoC, PATH-MCI uses a neurobiological model to streamline and structure its interventions for use in primary care practices.

Elders with depression and MCI may benefit from PATH-MCI. Preliminary results have demonstrated that PATH-MCI reduces depression and disability in elders with major or minor depression and mild cognitive deficits. PATH-MCI is not designed for patients with dementia as these patients may require additional assistance.

STUDY AIMS

The goals of the study are:

MONTHS 1-3:

1. Finalize the PATH-MCI Manual and establish feasibility of therapist training. We will train 4 LMSW/LCSWs: 2 will be trained in the PATH-MCI therapy, 2 will be trained in Supportive Psychotherapy. We will determine the success rate of training and number of hours needed to achieve PATH-MCI certification.

MONTHS 4-60

[figure not shown]
2. Assess PATH-MCI's reach, feasibility and acceptability: We will assess across conditions:
 - a. Reach: Number of patients screened, and those who meet inclusion criteria;
 - b. Feasibility: Number of patients who receive PATH-MCI or ST for mental health care and research procedures (timely referrals, assessments);
 - c. Acceptability: Patient's treatment satisfaction at 6, 12, 24, 36 and 52 weeks.

Benchmarks of the study progress: Feasibility: At least 75% of PATH-MCI participants will complete PATH-MCI. Acceptability: We will obtain treatment satisfaction score at the end of PATH-MCI treatment.

3. Preliminary Effectiveness: Over the course of 52 weeks, PATH-MCI patients, compared to patients receiving Supportive Psychotherapy, will have better global cognition and greater (effect size) and clinically significant reductions in disability and depression. Furthermore, better episodic memory and executive function will mediate the effects on cognitive outcomes

OVERVIEW OF DESIGN

Figure 1.

RECRUITMENT PROTOCOL

1. Patients are assessed and recruited from New York City Locations and Westchester.
 - Patients in NYC will be seen at [name].
 - Patients in Westchester will be seen at [name], Institute of Geriatric Psychiatry.
 - Patients at Montefiore will be seen at [name].
 - Note: There is no compensation for transportation expenses for patients. Any special cases must be discussed with [name] and [name].
 - Patients who are not able to meet in person may be assessed by phone or video.
2. Study staff may recruit using flyers, posters and referrals.
 - Flyers
 - NYC
 - Flyers for the study are placed in the waiting room of doctor's offices at [name], as permitted by the doctor's office. RAs must talk to the front desk before leaving flyers. Preferred floors are the 11th and 12th floors.
 - Flyers also can be placed in the elevators of the main hospital building on 72nd Street. Permission for this has been granted.
 - WP
 - Flyers can be placed in the waiting room of the Institute of Geriatric Psychiatry.
 - Flyers also may be distributed at events, eg. Salute to Seniors, etc.
 - Posters
 - A poster version of the flyer can be placed in the lobby of the [name] office.
 - RAs must communicate at all times with the building manager, [name]: [contact]. Inform her that we will be placing a poster in the lobby. Confirm with her the schedule for this, and that the easel obtained is the correct one to use.
 - Order posters through [name] or [name].
 - Referrals
 - We obtain referrals from different doctors. I.e. [name].
 - Make sure to follow up with the referral sources and to update referral sources about the patients they referred to us (meet criteria, did not meet, did not reach out to us, etc.).
 - We may also obtain referrals from sources, like the 4331 line at the Institute of Geriatric Psychiatry, and outside sources like JASA.

3. Phone screens

- When calling a potential patient, RA makes sure to first explain the study (quick overview) and answer any questions.

- Proceed with the phone screen, if a patient is interested in the study and agrees to the phone screen. Phone screens must be conducted with patients prior to scheduling a screening appointment
- Phone screen form for PATH-MCI study can be found at *I:\Cores\DMB\[name] STUDIES\Phone Screens*
- RAs must conduct phone screens on days and times that therapists and psychologists at the Institute are available. In case of an emergency, ie. a patient endorses suicidal ideation, the RA must communicate this information immediately to the therapists and psychologists present. RA must follow the suicide risk protocol. (See comprehensive SRA protocol at end of this document.)
- If the patient seems eligible from the phone screen (i.e. endorses some depression and low mood and some memory problems), schedule a screening session with the patient.

STUDY PROTOCOL

1. RAs obtain potential patient information from various referral sources.
2. RA contacts a potential patient to complete a phone screen about memory/neurological problems, mood/depressive symptoms, current involvement in treatment, and medical illnesses.
3. If the individual is interested in participating in our study and does not appear to meet exclusion criteria, the RA will invite the individual to come to our offices in White Plains or NYC, or to schedule a video or phone appointment, depending on the circumstances.
4. At the onset of the screening interview, the RA will conduct the informed consent process. If the patient has capacity to consent, the RA will conduct the screening assessment.
5. The RA will discuss the results of the assessment with [name].
6. If the patient is eligible, the RA will email the data manager with the individual's information.
7. The data manager will randomize the patient to either PATH-MCI or Supportive Therapy.
8. The data manager will notify [name] and the supervising therapist (not administering the intervention) about the randomization.
9. The supervising therapist will assign a therapist to the patient and inform the therapist to contact the patient to schedule first appointment (to take place following the baseline assessment).
10. The RA will schedule the baseline assessment with the patient and study partner. The patient will receive \$30, and the study partner will receive \$20 for the baseline assessment.
11. Team weekly meetings:
 - Review recruitment (specifically the numbers of positive screen patients)
 - Referrals
 - Tracking of all patients; we will discuss:
 - The status of assessments
 - The status of therapy sessions
 - The data manager will generate charts with recruitment progress.
12. The RA will conduct assessments with patients and their study partners at the following time points: 6, 12, 24, 36, and 52 weeks after the baseline assessment. Patients will receive \$30 (cash, check or gift card) for each set of assessments. Caregivers will be compensated \$20 (cash, check, or gift card) for each set of assessments.
 - Note: Genetic testing does not have an additional compensation.
13. If the caregiver does not come in person for assessments and they agree we can give their compensation to the patient, they must first sign the reimbursement form stating that it's okay for the patient to receive the money on their behalf. (See form I:\Cores\DMB\[name] STUDIES\PATH-MCI\Reimbursement Forms)

14. If the caregiver reimbursement can't be given to the subject, then we can do a payment requisition through WBG (during COVID-19), send a gift card, or send a money order. If possible, for money orders, send the caregiver a reimbursement form and self-addressed stamped envelope, so they can sign and mail the form back to us. Once the form is received, send a money order for the amount of the reimbursement.
15. All technology lent to patients will be returned to study staff.

Montefiore Medical Center Site

1. Patients will be recruited from Montefiore. When a patient is identified (by Montefiore) and agrees to be contacted by Cornell, a WCM RA will call the patient to schedule a screening appointment at the Blondell Site ([name]).
2. RAs will schedule Montefiore patients for Tuesdays, when there is space and [name] is there to supervise. There is room for one RA; if more than one RA needs to go, email [name] to see if she can find more room. Montefiore therapists will see study patients on Mondays and Fridays. Patients must sign both the Montefiore and WCM consent forms.
3. If a Montefiore subject signs the Genetics consent form, we will pay for transportation to Cornell for the blood draws. Blood draws can only be done at Cornell (White Plains or NYC), not Montefiore.
4. If RAs are there for the entire day, we will not pay for transportation, except for the cost of the parking garage.
5. If the RA is going to both the Montefiore and White Plains offices in the same day, we will pay for the transportation between the two sites (mileage for those driving, Uber/Lyft for those without a car).
6. RAs should bring data/work with them to Montefiore, regardless of how many patients they have scheduled, as there may be downtime if a patient screens out early. If only one patient is scheduled (am or pm), RAs should plan on being in White Plains the other half of the day.
7. Scheduling Patients at Montefiore: To aid the front desk in managing the patients coming in, please email [name] (and [name], so she can troubleshoot if [name] is away) every Friday the schedule of patients you are seeing the following week. These can be individual emails (ie. the RA's cases do not have to be on the same email as the therapist's cases). Please use the following format:

Schedule for [insert date]
9am- [patient name]
10 am- [patient name]
11am- [patient name]
1pm [patient name]
2pm [patient name]
3pm [patient name]

Email Sample:
Schedule for 12/10/2019
10am- [name]
2pm- [name]

In addition to helping the staff know whom to expect, this will facilitate locating the RA when a patient calls to confirm their appointment or if they come on the wrong day.

1

¹ As of June 2020, we are not recruiting patients from the Montefiore Medical Center site.

FULL SAMPLE COLLECTION AND PROCESSING PROTOCOL

1. All blood draws must be tracked in RedCap.
2. General Guidelines
 - Blood specimens will be collected at the following time points:
 - baseline, week 12, and week 52.
 - Baseline
 - ~16cc collected.
 - o 10cc DNA that will be serum frozen
 - o 6cc of red top tube
 - Week 12 and Week 52
 - ~ 6cc
 - DNA should only be collected from individuals who consent during screening visit to have their bio-specimens stored for future research.
3. Supplies
 - Lavender top tube will be collected at the baseline visit for DNA.
 - BD Vacutainer© K2 EDTA Plus Blood Collection Tubes (REF 366643)
 - 10 mL tubes
 - Red top tubes (SST) will be collected at the baseline, week 12 and 52.
 - BD Vacutainer© Serum Blood Collection Tubes (REF 367815)
 - 6 mL tubes
 - BD Vacutainer Blood Collection Set
 - Safety-Lok
 - 0.6 x 19mm x 305mm
 - BD Vacutainer one-use holder
 - Gloves
 - Alcohol pads
 - Large gauzes sterile
 - Medical tape sterile
 - Band-aids regular sized
 - Kimwipes
 - Waterproof thin sharpies

SAMPLE COLLECTION VISIT PROTOCOL

BASELINE VISIT:

Specimen Collection

1. Label one lavender tube with study name (PATH-MCI), patient #, date, visit #.
2. Label one red tube with study name (PATH-MCI), patient #, date, visit #.
3. Collect blood in labeled lavender tube for DNA (10mL tube).
4. Collected blood in one labeled red tube for processing (6ml tube).

Specimen Processing

1. Gently mix lavender tube collected.
2. Take the lavender tube to the deep freezer for immediate storage. Deep freezer settings -70 °C (-80 °C is also acceptable).
3. Allow red top tube to clot for 30 minutes standing up right at room temperature.
4. Centrifuge 4.4 RPM for 15 minutes until clot and serum are well separated. (This can either be chilled centrifuge or room temperature).
5. Pipette serum into 2mL aliquot tubes -approx. 1 mL in each tube.
6. Label the tubes with study name (PATH-MCI), patient #, date, visit #.
7. Store aliquot tubes in the deep freezer -70 °C (-80 °C is also acceptable).

WEEK 12 VISIT:

Specimen Collection

1. Label one red tube with study name (PATH-MCI), patient #, date, visit #.
2. Collected blood in one labeled red tube for processing (6ml tube).

Specimen Processing

1. Allow red top tube to clot for 30 minutes standing up right at room temperature.
2. Centrifuge 4.4 RPM for 15 minutes until clot and serum are well separated. (This can either be chilled centrifuge or room temperature).
3. Pipette serum into 2mL aliquot tubes -approx. 1 mL in each tube.
4. Label the tubes with study name (PATH-MCI), patient #, date, visit #.
5. Store aliquot tubes in the deep freezer -70 °C (-80 °C is also acceptable).

Week 52 Visit:

Specimen Collection

1. Label one red tube with study name (PATH-MCI), participant #, date, visit #.
2. Collected blood in one labeled red tube for processing (6ml tube).

Specimen Processing

1. Allow red top tube to clot for 30 minutes standing up right at room temperature.
2. Centrifuge 4.4 RPM for 15 minutes until clot and serum are well separated. (This can either be chilled centrifuge or room temperature).
3. Pipette serum into 2mL aliquot tubes -approx. 1 mL in each tube.
4. Label the tubes with study name (PATH-MCI), patient #, date, visit #.
5. Store aliquot tubes in the deep freezer -70 °C (-80 °C is also acceptable).

SAMPLE COLLECTION SITE PROTOCOL

NYC

1. Choose time for blood draw with the patient (Monday-Friday 9AM-5PM).
Location: [name]
2. Email [name] ([contact]), [name] ([contact]) about time slot, and cc [name] ([contact]) and [name] ([contact]).
3. In the email, send a copy of the consent form (study consent and genetics consent form), order form with subject name and assay form (iDrive link: I:\Cores\DMB\[name] STUDIES\PATH-MCI\Blood Draws\Forms for CTSC NYC). The order form needs to be signed by [name].
4. In the email **clarify to [name] and [name] to make sure they print the assay request form and include it with the sample.**
5. To fill out the assay request form, please follow the template included and previously completed assay request forms found on the iDrive.
6. The CTSC will take care of processing and storing of the samples.

***Note: Even though the CTSC is doing the processing, please make sure to track how many tubes, etc. they processed. Track in the WP about notebook.**

WHITE PLAINS:

1. When Blood Draw is conducted by RA who is Phlebotomy-Certified, follow the protocol called, "PATH-MCI Blood Processing Instructions" in the following iDrive location: I:\Cores\DMB\[name] STUDIES\PATH-MCI\Blood Draws
2. When Blood Draw is conducted by the Health Clinic/Lab in Westchester:
 - Make sure patient has been registered. All of our PATH-MCI patients should have an MRN provided by the registration done in On-Core, so their MRN number can be found on the On-Core spreadsheet. If they do not have an MRN assigned for some reason, first check with [name], but you can register the patient using the registration form found on the iDrive: I:\Cores\DMB\[name] STUDIES\PATH-MCI\Blood Draws\WP Registration for Venipuncture
 - Fill out a requisition form, which is located in the RA office 106. A sample of how this needs to be filled out is included below.
 - Once the patient has been registered, call [name] at the Clinical lab [name], to schedule a blood draw. Try to schedule the blood draw a day or two before the actual date. Phlebotomy lab hours are 8:30AM-2:30PM.

When you call [name], give her the following information:

 - Remind her of the study. Let her know that we only require the blood draw, not the processing.
 - Give the patient's first and last name

- Patient's date of birth
- Billing Code for Reqs: 12R
- WBS (account # for petty cash, etc.)
- MD name ([name])
- Diagnosis code
- Time and date of blood draw
- Once a date and time have been established, send [name] the requisition form with the date. You can fax this form to her at [name].
- Call to confirm appointment.
- The day of the appointment, walk the patient to the clinic, bring a sterile glove with you because you will be transporting the samples back with you. Obtain the sample from the phlebotomist, and immediately go to the lab to process the samples and store. Follow the specimen processing steps detailed above.

2

PATH-MCI Adverse Events – Safety Report Form

1. The Safety Report form is in RedCap.
2. RAs will keep this form with each research assessment they do and ask the patient at each visit whether they've experienced any new health or medical problems since their last visit (At Baseline, the time frame is since screening/consent.).
3. If the patient says yes, then complete the form (date of onset, severity, medical care received, etc.). The guidelines for assessing what constitutes an AE, the severity level, etc. can be found in the NIA guidelines (saved on the I drive: **(I:\Cores\DMB\[name] STUDIES\PATH-MCI\Adverse Events)**)
4. Therapists do not need to ask about new health problems. If the patient spontaneously says something in a session, the therapist should try to get as much of the above information as possible and let the RA know, so that the RA can complete this form.

² As of June 2020, the Westchester Division no longer has a clinical laboratory. Only a certified RA may collect samples at the White Plains site.

SUICIDAL IDEATION/ BEHAVIOR PROTOCOL

When a patient reports passive suicidal ideation on the MADRS Suicide Ideation item or the Scale for Suicide Ideation:

1. Complete a Suicide Risk Assessment
2. Reach out to the patient's study therapist. If the therapist is not available, reach out to [name] or another attending psychologist at the Institute.
3. The clinician will speak to the patient and assess the situation.

When a patient reports active suicidal ideation or any kind of suicidal behavior (suicide attempt, self-injurious behaviors, interrupted or aborted attempts, preparatory acts) on the MADRS Suicide Ideation item or the Scale for Suicide Ideation:

1. Complete a Suicide Risk Assessment.
2. Reach out to the patient's study therapist. RA or therapist also needs to reach out to [name] and inform him about the situation and ask him to assess the patient. If [name] is not available, contact another attending psychologist at the Institute ([name] needs to be informed later on about the situation.)
3. Preferably, the assessment by a clinician is done during the same phone call or when the patient is still in the office.

*Please see comprehensive SRA protocol at the end of this document.

RESEARCH ASSESSMENTS

The RA will describe the study, ask potential patients to sign consent, and administer a screening assessment to evaluate eligibility. Once this is confirmed, the RA will administer a baseline assessment. At this assessment, the RA will explain that follow-up assessments will be administered at 6, 12, 24, 36 and 52 weeks after the baseline assessment. The RA also explains that patients will be compensated \$30 for each set of completed assessments. Caregivers will be compensated \$20 for each set of assessments.

Inclusion Criteria:

1. Have a study partner.
2. Be 60-85 years old.
3. No antidepressants or have been on a stable dose of antidepressants for 12 weeks prior to start of study.

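### Cheap, optional improvement: the adverse event instruction questions only the patient, who is selected for mild cognitive impairment, and does not name the mandatory study partner as a source

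*Protocol*

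**What the plan says.** All of this is in the Protocol.

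- **Who is asked.** Under PATH-MCI Adverse Events – Safety Report Form, item 2, the RA is to "ask the patient at each visit whether they've experienced any new health or medical problems since their last visit". At baseline the look-back runs from screening or consent.
- **What triggers the form.** Item 3: "If the patient says yes, then complete the form".
- **Therapists.** Item 4: "Therapists do not need to ask about new health problems". The therapist gathers details and informs the RA "If the patient spontaneously says something in a session".
- **Who the patients are.** Inclusion Criteria 4 and 5 and Exclusion Criteria 2 and 4 select on a CDR of 0.5 and on a comparison of WTAR and HVLT scores. Capacity to consent is required.
- **The study partner.** A partner is compulsory (Inclusion 1, Exclusion 10). Study Protocol, step 10: "The RA will schedule the baseline assessment with the patient and study partner". Step 12: "The RA will conduct assessments with patients and their study partners at the following time points: 6, 12, 24, 36, and 52 weeks". Step 13 provides for partners who do not attend in person.
- **What is not shown.** Item 1: "The Safety Report form is in RedCap". Item 3 says that the rules for what counts as an adverse event and "the severity level, etc. can be found in the NIA guidelines". Conducting the Study Remotely refers to an Assessment Grid. None of these three is in the document.

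**The concern.** Each written route to the safety form starts with the patient: the patient answers the RA's question, or mentions something unprompted to a therapist. The trial recruits people with mild cognitive impairment, and the form asks for details such as when an event began, how severe it was and what care was received. Relying on the patient's unaided recall is a weak choice when a second informant is mandatory and already in contact with the RA.

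At stake is the completeness of general health event recording. An event that the patient does not recall, that nobody volunteers and that no unseen procedure picks up will not be on the form, and an analysis of the form data cannot restore it. Suicidality has its own detailed procedure and is outside this point.

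**Working it through.** The Protocol states no figure to reproduce here. The check sets the instructions side by side and derives the look-backs from the visit schedule.

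**1. Look-backs.** Scheduled assessments (Study Protocol, steps 10 and 12): weeks 0, 6, 12, 24, 36 and 52. Look-back = this visit minus the previous visit.

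- 6 − 0 = 6
- 12 − 6 = 6
- 24 − 12 = 12
- 36 − 24 = 12
- 52 − 36 = 16

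Sum: 6 + 6 + 12 + 12 + 16 = 52 weeks, and the longest is 16. If the week 36 visit were missed, the final look-back would be 52 − 24 = 28 weeks. The interval from screening to baseline is not stated and is left out.

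**2. Sources named in the adverse event section.**

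| Person | In contact with study staff? | Asked about new health problems? | Can start the form? |
|---|---|---|---|
| Patient | Baseline and weeks 6, 12, 24, 36, 52 | Yes (item 2) | Yes (item 3) |
| Therapist | Therapy sessions | Does not ask (item 4) | Relays what the patient volunteers |
| Study partner | Same time points (steps 10, 12) | Not mentioned | Not mentioned |

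Nothing bars the RA from recording what a partner volunteers, but nothing in items 2 to 4 solicits it.

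**3. Therapist relay in the long look-backs.** A parenthesis in Exclusion 5 suggests that treatment lasts about 3 months. If so, therapist relay would largely end before the 12- and 16-week windows. This is an inference, and the point does not depend on it.

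**4. What cannot be computed.** The number of missed events would need an event rate, the chance that a patient recalls and reports an event, and the chance that it arrives by another route. The Protocol gives none of these. The share of follow-up falling in long windows is no substitute. It would be the same in cognitively intact patients and the same after the partner is added, because the partner would be asked at the same weeks. It describes the schedule and measures neither the harm of the present rule nor the gain from changing it.

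**The case against.** The strongest reply is that nothing here is an error. No passage promises partner-based safety reporting, so items 2 and 3 contradict nothing. The form, the guidelines and the Assessment Grid may already name the partner, in which case only a summary instruction is incomplete. Patients have capacity to consent, people too medically unstable to enrol safely are excluded, and the Background says the therapy is not meant for dementia. Many patients will answer a direct question well, and the document contains no evidence that they do not.

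Most of this stands, and it limits the point to an optional improvement. It does not remove it, because who is asked and what triggers the form are fixed in writing, and the rule leaves out an available informant.

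The reply also says that the change is less simple than it looks. That is fair. Partners share the patient's time points but may not attend in person, and remote patient assessments are held with nobody else in the room. Some partners would have to be asked in their own phone or video contact.

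A reader might infer that adverse events are being missed, or that the safety comparison between arms is biased. The documents support neither. Under-recording is a risk and is not shown, the ascertainment rule is the same in both arms, and none of the goals under Study Aims is a safety comparison.

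**Conclusion.** The point holds as a low-cost, optional improvement to the written instruction. The RA solicits general health events only from the patient, over scheduled look-backs of up to 16 weeks, while a mandatory partner assessed at the same time points is not a named source. The possible consequence is under-recording in both arms, of a size that the Protocol does not allow anyone to state. No between-arm bias is claimed and no stated aim is affected.

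The conclusion assumes that visits occur as scheduled and that the documents not shown do not already direct the RA to ask the partner. If they do, what remains is a wording mismatch to put right.

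**What to change.** - **Item 2:** have the RA put the same question to the study partner at baseline and at each follow-up, within the partner's existing assessment contact, whether in person, by phone or by video.
- **Item 3:** let a yes from either the patient or the partner trigger the form.
- **Recording:** note the source or sources of each event (patient, partner, therapist relay) and count each event once.
- **If introduced mid-study:** record the date of change and report partner-only events separately, so that the patient-reported count stays comparable before and after. Footnotes dated June 2020 suggest that the study was already running, so this is likely to apply.
- **If the form, the NIA guidelines or the Assessment Grid already provide for partner reports:** align items 2 and 3 with them.

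**Cost.** One more question in the partner's contact, and a source field if the form has none. The downsides are a slightly longer partner contact, duplicates to merge and higher reported counts. Someone must check that consent covers asking the partner about the patient's health; the consent pages are not available here. When the partner does not attend, or the patient's session is private, the question has to go into the partner's own phone or video contact. A mid-study start puts two ascertainment methods into one count, which the source field and the date of change allow analysts to separate.
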